- D. The rehab consultant and the survivor begin the *check* phase of goal-plan-do-check. They review the goals and the actions plans, and proceed with a discussion about the do-check portion of the problem solving strategy. The rehab consultant guides the discussion using motivational interviewing and guided discovery techniques. If the plan was successfully implemented and the goals are achieved, next steps are discussed. If the plan was not implemented or the goals were not achieved, the rehab consultant will guide the survivor to modify the plan as necessary. The rehab consultant and the survivor discuss potential barriers to implementing the newly modified action plan and develop coping responses, using techniques for planning coping responses.
- E. The need for a second follow-up appointment is discussed and, if necessary, scheduled at a mutually convenient time. If the survivor seems to be struggling, a face-to-face follow-up might be scheduled. If a follow-up is deemed unnecessary at this time, the survivor is provided with information about how to access the rehab consultant in the future, should the need arise, and discharge occurs. The rehab consultant arranges a time for the research assistant to conduct a re-assessment of the outcome measures (Research Assessment 2), as well as a semi-structured interview for participant feedback.

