2.6 Step 6, Pilot Testing

In this step, we will implement the program evaluation plan established in Step 5, and will also include a pilot outcome evaluation to estimate the impact of the beta-RC on function and quality of life. We will implement and evaluate the beta-RC using a mixed method, single group study with a convenience sample of approximately 35 HNC survivors post primary cancer treatment, *recruited from the Princess*

*Margaret Cancer Center HNC clinics**, with inclusion and exclusion criteria and recruitment as described above in section 2.4.1. The procedures will be as described above in 2.4.1.2, with the following changes:

- a) An additional research assessment (Session 4) will be added. Session 4 will occur 1-2 months after Session 3; the participant will complete a follow-up assessment with the research assistant (approximately 60 minutes), either as a face-to-face visit or as a telephone interview. The assessment battery will be based on the tools described in Table 2.
- b) The intervention will include revisions based on feedback and observations from the pre-testing stage. The pilot testing version (beta RC) of the previously described intervention can be found in Table 3.
- c) The intervention will continue to be video recorded and reviewed by an investigator for fidelity. This will occur for the first 3 participants and then for every 5th participant who completes the intervention, starting with the 1st (1,2,3, then 8th, 13th, and so on). To explore survivor experiences with the RC, a survey will be administered during session 3, based on one-on-one semi-structured interviews carried out during the pre-testing phase. (approximately 30 minutes). The survey is included in Appendix B.

Participants will be remunerated \$25 for each *research* visit to the site to offset their transportation and parking costs. Additional *intervention-only* visits will not have any remuneration.

Quantitative data analysis will be exploratory and descriptive, and effect sizes will be calculated for all outcomes to help plan for a future, controlled trial. We will calculate means, standard deviations, and Cohen's *d* [39] effect size for normally distributed data. For non-normally distributed data, we will calculate medians, ranges, and a nonparametric effect size *r* using the formula $r^2 = z^2 / N$. [40] For qualitative analysis, all interviews will be audio recorded, transcribed verbatim, and analyzed using a

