Self-Efficacy	HNC RC Self-Efficacy Tool	There was no existing tool which adequately measured self-efficacy as it relates to the goals of this study. Therefore, a self-efficacy tool was created, using a 0-100 rating scale, based on Bandura (2006) "Guide to Constructing Self-Efficacy Tools" to measure the confidence of participants to achieve outcomes specific to this study. This tool is included as Appendix D.
Return to Work	Radiation Therapy Oncology Group (RTOG) Work Status Questionnaire [47]	The RTOG Work Status Questionnaire is a brief, patient-report tool that takes less than 5 minutes to complete. It was designed for use in RTOG trials, and psychometric properties have not been tested, but meets content validity criteria and sensibility criteria.
Goal Attainment	Goal Attainment Tool	Participants are asked about how well they currently perform a stated goal, which they develop in consultation with the rehabilitation consultant, how satisfied they are with this performance, and their confidence they can do the goal, and rate these on a scale of 0-100. A score of 0 represents low performance/satisfaction, and 100 represents the highest level of performance/satisfaction. This tool is included as Appendix C.
Patient Perspective Intervention Process	Rehab Consult Process Survey	Items for this survey were derived from questions posed in interview format during an earlier testing phase. 17 statements are scored using a 3-point Likert-type scale. Statements concerns intervention process issues such as timing, ease of use, and value of specific consult segments. This can be found in Appendix B.

Table 3: Pilot (beta) testing version of Rehabilitation Consult Process

Name	Process Steps	Methods
Orientation	A. A brief orientation (Appendix A) is given by the rehab consultant to orient the survivor to the reason for the consultation and the process.	Advance Organizer
Consultation	B. The rehab consultant reviews the brief HNC-specific functional evaluation (BRASH), and then consults with the survivor regarding the results. The survivor identifies the issues that are currently most important to him or her. If the participant has no goals, the rehabilitation closes the session by reinforcing that the options available if he/she has issues arising at a later time, and providing information on accessing the resource compendium.	Goal-setting Individualization Therapeutic alliance Facilitation Participatory problem solving

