Reminder	
A. A telephone reminder regarding the follow-up appointment is made 24 hours in advance.
	Advance organizer Individualization
Re-Orientation	
B. The rehab consultant phones at the designated date and time and confirms with the survivor that the appointment is still convenient. The rehab consultant re-orient the survivor to the RC process.
	Facilitation Individualization
Checking	
C. The rehab consultant and the survivor begin the check phase of goal-plan-do-check. They review the goals and the rehab consultant
	Self monitoring of behavior Individualization Goal setting Motivational interviewing

	
re-administers the goal attainment tool. Subsequently, the actions plans are reviewed and they proceed with a discussion about the do-check portion of the problem solving strategy. The rehab consultant guides the discussion using motivational interviewing and guided discovery techniques. If the plan was successfully implemented and the goals are achieved, next steps are discussed. If the plan was not implemented or the goals were not achieved, the rehab consultant will guide the survivor to modify the plan as necessary. The rehab consultant and the survivor discuss potential barriers to implementing the newly modified action plan and develop coping responses, using techniques for planning coping responses.
	
techniques Self monitoring of behaviours Self re-evaluation Goal setting Implementation intentions Planning coping responses Guided discovery Verbal persuasion

Discharge or Further Follow-up
	
D. The need for a second follow-up appointment is discussed and, if necessary, scheduled at a mutually convenient time. If the survivor seems to be struggling, a face-to-face follow-up might be scheduled. If a follow-up is deemed unnecessary at this time, the survivor is provided with information about how to access the rehab consultant in the future, should the need arise, and discharge occurs.
	
Individualization Facilitation Guided discovery Verbal persuasion Implementation intentions Planning coping responses

Figure 1: Timeline

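### Does the Step 6 pilot plan a qualitative analysis with no interviews to feed it?

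*Combined protocol and SAP*

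**What the plan says.** Section 2.6 describes the beta-RC pilot as a mixed-method, single-group study of about 35 survivors. Its analysis paragraph ends with the qualitative part: "For qualitative analysis, all interviews will be audio recorded, transcribed verbatim, and analyzed using a" hybrid approach, deductive and inductive, in two phases.

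The procedures come from elsewhere: "The procedures will be as described above in 2.4.1.2, with the following changes". Three changes follow.

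- Item a) adds a fourth session, a further research assessment.
- Item b) replaces the intervention: "The pilot testing version (beta RC) of the previously described intervention can be found in Table 3".
- Item c) keeps video recording for fidelity review and, for survivor experience, says that "a survey will be administered during session 3, based on one-on-one semi-structured interviews carried out during the pre-testing phase". A note of about 30 minutes is attached.

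Table 2 describes the survey: "Items for this survey were derived from questions posed in interview format during an earlier testing phase", and "17 statements are scored using a 3-point Likert-type scale".

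In section 2.4, step E of the alpha follow-up has the consultant arrange the second research assessment "as well as a semi-structured interview for participant feedback". The matching step D of Table 3 ends with information on how to reach the consultant later, "should the need arise, and discharge occurs".

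**The concern.** Read in order, the plan appears to analyse data that it never collects. The analysis sentence speaks of all interviews, but none of the four Step 6 sessions contains one. The alpha process arranged a feedback interview, and the nearly identical last step of the beta process does not mention it. What remains for survivor experience is a closed-item survey, which gives nothing to transcribe.

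The findings go to the Advisory Panel, which recommends further modifications before a version is finalised for future evaluation. If the qualitative arm were empty, the Panel would see how survivors rated each part of the consultation but not their reasons. An interview not held during the pilot is hard to recover afterwards.

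**Working it through.** The plan states no figure to reproduce, so this is a comparison of passages with a few counts.

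**1. Search for a Step 6 interview.**

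| Place | What it provides | Qualitative interview? |
|---|---|---|
| Section 2.4.1.2 (inherited) | Research assessments, consultation, follow-up call, post-intervention survey | None named |
| Section 2.6, item a) | Session 4 assessment; a telephone interview is one way of giving the battery | None named |
| Section 2.6, item b), and Table 3 | Beta intervention steps | None named |
| Section 2.6, item c), and Table 2 | Session 3 survey, 17 statements, 3-point scale | None named; interviews are placed in pre-testing |

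The count over Sessions 1 to 4 is 0 + 0 + 0 + 0 = 0. The mismatch is therefore real on the text.

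**2. Does Table 3 show that the interview was dropped?** It does not. In alpha step E, one sentence schedules two things: the second research assessment and the interview. Table 3 omits that whole sentence. Yet the post-intervention assessment plainly continues in Step 6, because section 2.4.1.2 is inherited and item a) times Session 4 from Session 3. Table 3 lists intervention steps and methods, and research scheduling was left out as a block. Its silence says nothing specific about the interview.

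**3. Does absence from section 2.4.1.2 show it?** That is no stronger. Section 2.4.1.2 lists no feedback interview for pre-testing either, although step E arranged one there. A zero count from that section would wrongly give zero for pre-testing too.

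**4. Which interviews could the sentence mean?** The only semi-structured interviews named in section 2.6 are those of pre-testing, on which the survey is based. For pre-testing, section 2.4.1.2 promises only descriptive analysis, so the sentence in section 2.6 is the only coding method for interviews anywhere in the text. It may refer to those interviews. It may be wording left from a stage when Step 6 had interviews. Or it may rely on Appendix B or the Step 5 evaluation plan, whose contents are not in the copy reviewed.

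**5. The note of 30 minutes.** If it is the survey's duration, it allows 30 / 17 = 1.8 minutes per statement. That is long for three-level ratings and may point to discussion or open items. If it describes the earlier interviews, it is a leftover. The text does not decide.

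**6. What the Panel receives without new interviews.** The survey gives at most 17 x 35 = 595 ratings. This is a ceiling: it assumes that all of about 35 participants reach Session 3 and answer everything, while Table 3 closes the consultation for those with no goals. Under the inherited section 2.4.1.2, review of recordings also extracts what went well and what was difficult for each participant reviewed, and the research assistant records respondent burden and how easy the tools are to use. Fidelity review covers participants 1, 2, 3, 8, 13, 18, 23, 28 and 33, which is 9 if 35 complete.

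**7. Cost of adding interviews.** The documents give no length, so assume 5 to 15 minutes each. Then 35 x 5 = 175 minutes = 2.9 hours, and 35 x 15 = 525 minutes = 8.75 hours of audio to transcribe and code.

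**The case for a change.** The strongest case for a change is that the sentence sits in the Step 6 analysis paragraph of a study called mixed-method, and that the findings feed decisions made after the pilot. Pre-testing planned both a process survey and an interview, so a survey in Step 6 does not by itself imply that the interview was replaced. Table 2 lists the tools and the contents page lists the appendices, and neither names an interview guide. Session recordings are for process and fidelity review and are never called interviews. A literal-minded team could finish the pilot with no transcripts.

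Much of this stands: the sentence is loosely placed and its source is not named. What does not follow is that the analysis is empty or that the pilot needs more data. Item c) states how survivor experience is to be explored, and Table 2 explains that the survey items came from the interview questions. That reads as a deliberate move from interview to survey, which gives up depth for lower burden in a pilot that already has three research assessments per participant. Preferring open questions is reasonable, but it is a preference. Deleting the sentence as obsolete would do harm, because pre-testing interviews would then have no stated coding method.

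**Conclusion.** The concern is correct that section 2.6 does not say which interviews it means. It does not show a defect that alters a result. The possible readings are pre-testing interviews, leftover wording, or a source in Appendix B or the Step 5 plan. Under each, analysts would apply the hybrid method to whatever interviews were recorded and summarise the survey under the exploratory, descriptive approach that section 2.6 already sets for quantitative data. Naming the source would be editorial tidying. Adding interviews would be a trade-off, at an assumed 2.9 to 8.75 hours of audio.

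The effect on means, standard deviations, Cohen's d and the nonparametric effect size is nil. The conclusion rests on two assumptions: that the Session 3 survey is the intended measure of survivor experience in Step 6, as item c) states, and that no unseen part of the Step 5 plan makes interview findings decisive for adopting or rejecting the intervention. No change to the plan follows.

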3.0 DISCUSSION

This project brings together the diverging views of rehabilitation specialists, focused on long-term real-world function, with those of cancer specialists, focused on acute treatment and episodic symptom management. We have set out to bring those views together to develop a clinically effective and cost-

Development and pilot evaluation of rehabilitation consult for survivors of head and neck cancer

effective rehabilitation intervention that integrates seamlessly with an existing cancer care system.

Survivors of HNC have among the most complex rehabilitation needs of all cancer patients because of the anatomical complexity of the head and neck region. The RC is expected to improve knowledge and uptake of rehabilitation resources and strategies in survivors of HNC, and thereby improve function and quality of life. The RC will be designed to ensure the components are readily modifiable for use beyond the regional cancer centres within which they were developed. Further, we believe that HNC serves as an ideal incubator for development of the RC. If it is effective in cancer patients with such high and diverse needs, it is expected that this project will produce a toolkit that will be adaptable for other types of cancer in other jurisdictions.

FUNDING STATEMENT

This work is supported by the Canadian Cancer Society Research Institute Innovation Grant (#702896).

The background work was made possible by a University of Toronto Faculty Research Grant, the Grant Miller Cancer Grant.

Modifiable	
Awareness of rehab needs/risk
 
Communication style
 
Coping style
 
Healthcare team engagement and buy-in
 
Knowledge about association among needs/issues
 
Knowledge about condition
 
Knowledge about metacognitive strategy use
 
Knowledge about symptom management and resources
 
Local processes
 
Physician referral processes
 
Physician support and participation (awareness of rehab consult, recommendations and clearance)
 
Pre-existing mood/behavior
 
Self efficacy
	
Action planning
 
Addictions – presence or absence
 
Attitudes/biases towards HNC survivors
 
Availability of and access to relevant resources (particularly clinicians)
 
Community resources
 
Coping habits
 
Developing strategies
 
Dietary habits
 
Energy Budgeting
 
Exercise habits
 
Expectations
 
Goal setting and action planning
 
Health care professionals knowledge about rehab and head and neck cancer treatment
 
Problem solving
 
Rehab resources
 
Self regulation/self evaluation
 
Substance use, particularly smoking, - presence
	
Aesthetic outcomes
 
Body image/body satisfaction
 
Cardiovascular capacity
 
Chewing/mastication
 
Cognitive impairments
 
Dental issues
 
Digestive system functioning
 
Dry mouth
 
Fatigue
 
Fibrosis
 
Instrumentation care (eg. Trach, feeding tube, etc)
 
Intimacy
 
Joint mobility
 
Late effects
 
Lymphedema/edema
 
Mental health (eg. Anxiety, depression, mood)
 
Mouth opening
 
Muscle strength
 
Range of motion (ROM) – neck, upper extremity, mouth/jaw
 
Neuropathies/Sensory issues
 
Pain
	
Decreased employment
 
Decreased functional status (Activities of Daily Living or ADLs)
 
Decreased health status
 
Decreased participation and engagement in personally-meaningful life areas
 
Decreased psychosocial function
 
Decreased role function

		or absence	Personality changes Respiratory issues Senses (ie. Smell, taste, touch, sight, hearing) Sexuality Speech Swallowing Voice Weight loss	
Difficult to Modify	Age Disease site Education level Personality Sex Socioeconomic status/finances Treatment received	Culture (of survivor) Familial/caregiver support Geographic location – rural vs urban Hospital type (eg cancer centre vs tertiary care centre) Language Living/workplace conditions (e.g. exposure to second-hand smoke, exposure to carcinogenic substances at work unknowing or without proper protection gear, etc.)		

Items in *italics* are targeted for change.

Items in the “Determinants” column refer to both clinician and provider, where applicable, unless otherwise stated.

Table 2. Outcome Measures

Construct	Instrument(s)	Description and Psychometric Properties
Health-related Quality of Life	Medical Outcomes Study 36-item Short-Form Health Survey (SF-36) [42,43]	SF-36 a widely used, generic, patient-report measure created to assess health-related quality of life (HRQOL). It consists of 8 domains: Physical Functioning, Role limitations due to Physical problems, Bodily Pain, General Health Perceptions, Social Functioning, General Mental Health, Role limitations due to Emotional problems, and Vitality. SF-36 has been widely tested, and, with the exception of the Social Functioning subscale, has excellent internal consistency and interrater reliability; SF-36 has adequate to excellent convergent validity with a number of functional and HRQoL scales.
	The Functional Assessment of Cancer Therapy-Head and Neck Version 4 (FACT-H&N) [44]	Self-report reliable and valid quality of life questionnaire. The scale consists of a core FACT-G (General) questionnaire that covers four domains: physical, social/family, emotional, and functional. The scale is supplemented by a head and neck cancer specific subscale. Items are rated on a 0 (Not at all) to 4 (Very much) Likert scale and scores are calculated to produce subscale scores for each domain. It is reliable and valid in patients with HNC, scores correlating with treatment status and global performance status.
Participation	Reintegration to Normal Living Index (RNL) [45]	The RNL consists of 11-items covering areas such as recreational and social participation, community mobility, family roles and other relationships. It has high internal consistency, moderate interrater reliability, and is correlated with measures of quality of life and well being.
Self-Efficacy	HNC RC Self-Efficacy Tool	There was no existing tool which adequately measured self-efficacy as it relates to the goals of this study. Therefore, a self-efficacy tool was created, using a 0-100 rating scale, based on Bandura (2006) "Guide to Constructing Self-Efficacy Tools" to measure the confidence of participants to achieve outcomes specific to this study. This tool is included as Appendix D.
Return to Work	Radiation Therapy Oncology Group (RTOG) Work Status Questionnaire [47]	The RTOG Work Status Questionnaire is a brief, patient-report tool that takes less than 5 minutes to complete. It was designed for use in RTOG trials, and psychometric properties have not been tested, but meets content validity criteria and sensibility criteria.
Goal Attainment	Goal Attainment Tool	Participants are asked about how well they currently perform a stated goal, which they develop in consultation with the rehabilitation consultant, how satisfied they are with this performance, and their confidence they can do the goal, and rate these on a scale of 0-100. A score of 0 represents low performance/satisfaction, and 100 represents the highest level of performance/satisfaction. This tool is included as Appendix C.
Patient Perspective Intervention Process	Rehab Consult Process Survey	Items for this survey were derived from questions posed in interview format during an earlier testing phase. 17 statements are scored using a 3-point Likert-type scale. Statements concerns intervention process issues such as timing, ease of use, and value of specific consult segments. This can be found in Appendix B.

Table 3: Pilot (beta) testing version of Rehabilitation Consult Process

Name	Process Steps	Methods
Orientation	A. A brief orientation (Appendix A) is given by the rehab consultant to orient the survivor to the reason for the consultation and the process.	Advance Organizer
Consultation	B. The rehab consultant reviews the brief HNC-specific functional evaluation (BRASH), and then consults with the survivor regarding the results. The survivor identifies the issues that are currently most important to him or her. If the participant has no goals, the rehabilitation closes the session by reinforcing that the options available if he/she has issues arising at a later time, and providing information on accessing the resource compendium.	Goal-setting Individualization Therapeutic alliance Facilitation Participatory problem solving
Goal-setting	C. The survivor and the rehab consultant work collaboratively to make goal statements based on issues identified by the survivor as most important to him or her. The rehab consultant administers a goal attainment tool (Appendix D) wherein the participant rates his or her current performance, satisfaction, and confidence with the goals.	Goal-setting Individualization Therapeutic alliance Facilitation Participatory problem solving Cognitive strategy training
Teach cognitive strategy	D. The rehab consultant teaches the global problem solving strategy, Goal-Plan-Do-Check (Meichenbaum, 1971).	
Action Planning, Planning Coping Responses, and Introduction to Resources	E. Using the Goal-Plan phases of the problem solving strategy, the rehab consultant and the survivor develop an action plan to meet the identified goals. The rehab consultant uses motivational interviewing techniques (eliciting change talk, evoking motivation to make positive changes (Miller & Rollnick, 1991) and guided	Individualization Therapeutic alliance Facilitation Participatory problem solving Motivational interviewing techniques Framing Guided discovery Implementation intentions Planning coping responses

	
discovery techniques (ask don't tell, coach don't adjust, make it obvious, and one thing at a time (Polatajko & Mandich, 2004)). The rehab consultant reviews the rehabilitation resources of which the survivor may already be aware, or accessing. The rehab consultant reviews the study website (resource compendium) (www.hncrehab.ca), with the survivor, for future use, and facilitates the assembly of resources previously unknown to the survivor, which are necessary to implement the survivor's plans. Also as part of the planning process, the survivor identifies potential barriers to implementing the action plan and develops coping responses, using planning coping responses techniques (Marlatt & Donovan, 2005), all facilitated by the rehabilitation consultant.
	Verbal persuasion
Execution	
F. Facilitated by the rehab consultant, the survivor reviews his or her goals and action plan for clarity, and is encouraged to execute (do) his or her plan. Follow-up appointment is scheduled for between 2 and 10 weeks later, at a mutually convenient time. This may be in person, or via telephone, as per survivor's preference.
	Implementation intentions Planning coping responses
Follow-Up Process		
Reminder	
A. A telephone reminder regarding the follow-up appointment is made 24 hours in advance.
	Advance organizer Individualization
Re-Orientation	
B. The rehab consultant phones at the designated date and time and confirms with the survivor that the appointment is still convenient. The rehab consultant re-orient the survivor to the RC process.
	Facilitation Individualization
Checking	
C. The rehab consultant and the survivor begin the check phase of goal-plan-do-check. They review the goals and the rehab consultant
	Self monitoring of behavior Individualization Goal setting Motivational interviewing

	
re-administers the goal attainment tool. Subsequently, the actions plans are reviewed and they proceed with a discussion about the do-check portion of the problem solving strategy. The rehab consultant guides the discussion using motivational interviewing and guided discovery techniques. If the plan was successfully implemented and the goals are achieved, next steps are discussed. If the plan was not implemented or the goals were not achieved, the rehab consultant will guide the survivor to modify the plan as necessary. The rehab consultant and the survivor discuss potential barriers to implementing the newly modified action plan and develop coping responses, using techniques for planning coping responses.
	
techniques Self monitoring of behaviours Self re-evaluation Goal setting Implementation intentions Planning coping responses Guided discovery Verbal persuasion

Discharge or Further Follow-up
	
D. The need for a second follow-up appointment is discussed and, if necessary, scheduled at a mutually convenient time. If the survivor seems to be struggling, a face-to-face follow-up might be scheduled. If a follow-up is deemed unnecessary at this time, the survivor is provided with information about how to access the rehab consultant in the future, should the need arise, and discharge occurs.
	
Individualization Facilitation Guided discovery Verbal persuasion Implementation intentions Planning coping responses

Figure 1: Timeline
